## 1. SYNOPSIS

Study Title	Investigation of cerebrospinal fluid (CSF) pharmacokinetics of ondansetron
Brief Title	CSF PK of ondansetron
Objective	To determine human cerebrospinal fluid (CSF) and plasma pharmacokinetic parameters of 5HT3R antagonist ondansetron after intravenous administration.
Hypothesis	Approaches to enhance CNS penetration of ondansetron might be useful for obtaining analgesic effect with 5HT3R antagonists in neuropathic pain.
Study Period	Planned enrollment duration: Approximately 3 months Planned study duration: One (4-hour) study day per subject, on the day of knee/hip arthroplasty surgery.
Number of Subjects	15 evaluable subjects having elective hip or knee arthroplasty with spinal anesthesia from up to 30 consented subjects.
Study Treatment	Single intravenous 15-min infusion of 16mg ondansetron.
Study Design	Prospective, open-label, pharmacokinetic pilot study.
Inclusion and Exclusion Criteria	
Inclusion criteria:
 
 
1. Age between 18 and 70 years old;
 
2. Patients planned to undergo hip or knee arthroplasty with spinal anesthesia;
 
3. Ability to provide informed consent
 
 
Exclusion criteria:
 
 
4. Not giving consent to participate in the study;
 
5. Patients with history of or current hepatic or renal insufficiency;
 
6. Patients with <math>BMI \geq 33</math>;
 
7. Patients with heart failure or active arrhythmias;
 
8. Patients with severe systemic disease that is a constant threat to life;
 
9. Contraindication or allergy to ondansetron;
 
10. Pregnancy or lactation.
 
11. Prisoners
 

Measurements	
Ondansetron CSF and plasma Pharmacokinetics:
 
 
1. A single 4-mL CSF sample per subject.
 
2. Serial blood sampling at 0 (pre-infusion), 15, 30, 60, 120, and 180 min after ondansetron administration.
 
 
Genotyping: A blood sample will be obtained at baseline for determining the following single nucleotide polymorphisms (SNPs) as confounders of ondansetron PK parameters:
 
 
1. ABCB1 gene (p-Glycoprotein transporter): C3435T, G2677T, T-129C, G1199A, C1236T.
 

	2. In SLC22A1 gene (OCT1 transporter): R61C, C88R, G401S, M420del, G456R.

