## 2. STUDY PROTOCOL

### 2.1 Background and Significance

Neuropathic pain [NeuP] affects 7-8% of the adult population and is particularly challenging to treat. More than 30% of neuropathic pain patients continue to suffer despite treatment; and there is clearly an urgent need for new treatment approaches. However, the translation of findings from current neuropathic pain animal models to clinical trials have been extremely disappointing, with multiple pre-clinically promising agents failing to show robust clinical effectiveness; suggesting that 1) additional pharmacodynamic (PD) and pharmacokinetic (PK) factors responsible for effective animal-to-human translation need to be considered, and 2) because of a large inter-subject variability in pain mechanisms and treatment response, an “all-comers” approach is suboptimal in yielding significant leaps forward in the success of treating neuropathic pain. Therefore, addressing possible PK and PD translational gaps and investigating genotypic and phenotypic predictors of response can improve the translational process and allow more effective drug discovery and individual analgesic tailoring in neuropathic pain.

Serotonergic 5HT3Rs in the central nervous system (CNS) have been identified as a promising pharmacological target in neuropathic pain [1, 2]. After peripheral nerve damage the character of serotonergic descending modulation changes from inhibitory to facilitatory through 5HT3Rs in the spinal cord [3, 4]. This finding is supported by studies demonstrating that intrathecal (IT) administration of 5HT3R antagonists such as ondansetron alleviates mechanical and thermal hypersensitivity in animal nerve injury models [1, 5]. In contrast to IT administration, systemic ondansetron does not produce consistent analgesia. However, this is not surprising, considering that CNS concentrations of 5HT3R antagonists such as ondansetron highly depend on the expression level of P-glycoprotein (Pgp) - an efflux transporter at the capillaries of the blood-brain barrier (BBB) which transports xenobiotics out of the CNS to the systemic circulation [6, 7].

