Clinical trials performed with 5-HT3 antagonists for treating pain have yielded mixed results. Two studies with tropisetron in fibromyalgia have yielded somewhat positive results, but had methodological shortcomings, and a well-designed tropisetron study in 30 patients with low back pain was negative. Two studies with ondansetron in neuropathic pain were overall negative, but in one of the studies, pain reduction 2h after ondansetron administration was larger than with placebo [8, 9]. In both these studies individual data (personal communication with the authors) indicate that certain patients had good analgesic response to intravenous ondansetron, warranting further investigation into the individual response profiles.

We suggest that one of the caveats leading to unsuccessful clinical translation of the promising animal data is related to the essential pharmacokinetic criterion that probably determined the lack of efficacy of systemic ondansetron in rodents - i.e. inability to achieve effective concentration at the site of action. We propose that sufficient exposure of 5HT3R antagonists at their site of action in the CNS, as well as the choice of appropriate pain condition are of key importance for testing the clinical effectiveness of 5HT3R antagonists in NeuP. Consequently, the goal of the project is to establish detailed CNS pharmacokinetic (PK) parameters of ondansetron, to provide sound basis for a future study with enhanced CNS penetration of ondansetron in neuropathic pain.

Two genetic factors shown to affect the pharmacokinetics and the antiemetic efficacy of ondansetron are 1) polymorphism in the ABCB1 gene expressing P-glycoprotein, a transporter which controls the transport of ondansetron to the CNS via the BBB; and 2) polymorphism in the SLC22A1 gene expressing organic cation transporter-1 (OCT1), a transporter responsible for hepatic uptake of

ondansetron. We will collect the genetic data on these polymorphisms to account for inter-subject variability in pharmacokinetic parameters of ondansetron.

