### 2.5.2 Study Period

Subjects will be studied in the Department of Anesthesiology of Washington University-Barnes Jewish Hospital, prior to and during their scheduled hip or knee arthroplasty surgery.

An intravenous catheter will be inserted in an arm for drug administration and in the opposite arm for obtaining blood samples to evaluate the plasma concentrations of ondansetron. The former will be used also for pre/intraoperative fluids and anesthesia drug administration.

At baseline, a 5ml blood sample will be collected for pharmacokinetics and another 5ml sample for genetic analysis.

Ondansetron will be administered in a 16mg single dose as a 15 min intravenous infusion. Although up to 32mg doses of intravenous ondansetron have been used in clinical trials, 16mg is currently the highest FDA-recommended dose for single administration. Two additional 4mg doses of either IV or oral ondansetron will be allowed for postoperative nausea and vomiting treatment in the study subjects, at the discretion of the treating physicians.

A single CSF sample of 4ml will be collected immediately after spinal needle insertion and before administration of spinal anesthesia. This procedure is routinely performed in the holding area, approximately 30 min before the patient enters the operating room (OR) for planned surgical procedure with spinal anesthesia. As only one sample of CSF is obtained from each subject, the timing of the infusion will be scheduled at approximately 30, 60, or 120 min before planned pre-surgical spinal needle insertion. This will allow 3 time-points of CSF samples from the aggregate study cohort. For determination of the above timing, the patients will be randomized in blocks of 3 for infusion timing (approximately 5 subjects per block), to allow even distribution of CSF PK sample time-points.

Six 5mL serial venous blood samples will be obtained from all subjects at 0 (pre-treatment), 15, 30, 60, 120, and 180 min from the beginning of infusion in each patient, regardless of timing for CSF sampling. The samples will be put on ice, centrifuged for 10 min at 5000 rpm. Plasma will be transferred to two 1.5mL vials and stored at -80°C until analysis by HPLC-MS.

The CSF ondansetron pharmacokinetic profile will be constructed using population PK approach, according to the exact time of CSF sampling. Ondansetron concentration in plasma (expected 40-120ng/mL) and CSF (expected 3-12ng/ml) will be determined by HPLC-MS-MS analysis [10].

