### **2.5.4 Observations and Measurements**

#### **2.5.4.1 Primary Outcome Measures**

##### Primary outcome:

Plasma and CSF concentrations of ondansetron, and CSF to plasma concentration ratio.

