#### **2.5.4.3 Pharmacokinetic data analysis:**

Individual plasma concentration-time data will be analyzed using non-compartmental methods. The following PK parameters will be calculated and compared between subjects with different transporter expression level: volume of distribution, systemic clearance, the elimination half-life, and the total area under the concentration-time curve. In addition, a compartmental population-based pharmacokinetic model will be constructed, which will evaluate inter-subject variability in pharmacokinetic parameters. Preliminary assessment of published data indicates that the systemic disposition of ondansetron follows two-compartment model with linear elimination following intravenous administration in humans.

The population model will include a “CSF distribution compartment”, which will allow for the estimation of the partition coefficient between the plasma and CSF. The effect of transporter expression level phenotypes on individual pharmacokinetic parameters will be evaluated using a standard covariate analysis. Utilization of population approach will allow for estimation of population mean and individual patients parameters. This pharmacokinetic methodology is especially useful for analysis of sparse data (i.e., a single CSF sample from each patient).

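### The CSF:plasma ratio and partition coefficient use plasma drug uncorrected for protein binding, so their absolute size cannot by itself show how far CNS penetration is restricted

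*Combined protocol and SAP*

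**What the plan says.** The primary outcome (2.5.4.1) is "Plasma and CSF concentrations of ondansetron, and CSF to plasma concentration ratio". Section 2.5.2 gives the expected values: "Ondansetron concentration in plasma (expected 40-120ng/mL) and CSF (expected 3-12ng/ml) will be determined by HPLC-MS-MS analysis [10". On plasma handling, the same section says, after icing and centrifugation: "Plasma will be transferred to two 1.5mL vials and stored at -80°C until analysis by HPLC-MS". It describes no ultrafiltration, dialysis or other step to isolate unbound drug.

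Section 2.5.4.3 adds a CSF compartment to the population model, "which will allow for the estimation of the partition coefficient between the plasma and CSF". The Statistical Methodology row of the Synopsis says the same in substance. Neither place has a term for the unbound fraction.

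Protein binding and free drug are not mentioned anywhere in the protocol. Albumin is measured (2.5.1) only in subjects with known or suspected renal or hepatic disorder, to decide eligibility.

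The purpose of the work is stated in two places. The Synopsis hypothesis reads: "Approaches to enhance CNS penetration of ondansetron might be useful for obtaining analgesic effect with 5HT3R antagonists in neuropathic pain". Section 2.1 says the PK results are "to provide sound basis for a future study with enhanced CNS penetration of ondansetron in neuropathic pain", and it names P-glycoprotein efflux as a main determinant of CNS concentration.

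**The concern.** CSF contains little protein, so the drug measured there is close to unbound. Plasma assayed as planned gives bound plus unbound drug. The ratio of the two then reflects how much drug is bound in plasma as well as how readily it crosses into CSF. A drug that crosses freely but is partly bound would still give a ratio below 1.

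This matters for the use named in the Synopsis and 2.1. The room for enhancing penetration is the gap between the unbound CSF:plasma ratio and 1. The total ratio does not measure that gap, and neither does a partition coefficient built on the same plasma input. A follow-on study (2.5.5 mentions 60-80 further patients) that took its scope for enhancement from the raw ratio could start from a gap that is too large.

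**Working it through.** The plan states no ratio or unbound fraction, so there is no figure of its own to reproduce. The check asks what its expected concentrations imply.

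**Inputs**
- Expected plasma 40-120 ng/mL and CSF 3-12 ng/mL (2.5.2).
- Unbound fraction in plasma, fu: not in the documents. It is an assumption, varied from 0.1 to 1.0.
- CSF drug treated as essentially unbound: general pharmacology, not in the documents.

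**Step 1: implied total ratio, R = CSF / plasma**
- Low with low: 3/40 = 0.075
- High with high: 12/120 = 0.10
- Midpoints: 7.5/80 = 0.094
- Extreme pairings: 3/120 = 0.025 and 12/40 = 0.30

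**Step 2: split the ratio**

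Let U be the unbound CSF:plasma ratio, with U = 1 meaning no net barrier. Then R = fu × U, so U = R / fu.

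| Assumed fu | U at R = 0.075 | U at R = 0.10 |
|---|---|---|
| 0.1 | 0.75 | 1.00 |
| 0.2 | 0.38 | 0.50 |
| 0.3 | 0.25 | 0.33 |
| 0.5 | 0.15 | 0.20 |
| 0.8 | 0.09 | 0.13 |
| 1.0 (no binding) | 0.075 | 0.10 |

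Uncorrected, the shortfall from free equilibration is 1/0.10 = 10-fold to 1/0.075 = 13-fold. At fu = 0.2 it is 1/0.50 = 2-fold to 1/0.375 = 2.7-fold. Binding alone accounts for the whole shortfall only when fu = R or lower, that is at 0.075 to 0.10. With the extreme pairings at fu = 0.3, U runs from 0.025/0.3 = 0.08 to 0.30/0.3 = 1.00.

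**Step 3: does the population model separate the two?**

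In a simple CSF compartment driven by plasma, the driving term is the partition coefficient times plasma concentration. With plasma as total drug, that coefficient is the product fu × U. Different sampling times help with the rate of transfer but leave the product unsplit. If the plasma input is fu × plasma concentration instead, the coefficient becomes U.

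**Step 4: does it touch the genotype comparison?**

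Under a common fu the factor cancels. With U of 0.6 in one group and 0.3 in another, (fu × 0.6)/(fu × 0.3) = 2.0 at fu 0.1, 0.3 or 0.5.

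**The case against.** The strongest reply is that the plan never draws the conclusion at risk. Its stated objective (2.3) is feasibility. The P-glycoprotein premise in 2.1 rests on cited earlier work, not on the ratio to be measured. A reader might infer that a ratio near 0.1 will be reported as 10% penetration and as support for a P-glycoprotein strategy, but no passage says so.

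Further parts of the reply also stand:
- **Transporters have their own route.** Section 2.5.4.3 says: "The effect of transporter expression level phenotypes on individual pharmacokinetic parameters will be evaluated using a standard covariate analysis". A common unbound fraction cancels there. Differences between subjects in binding would add noise, but would bias the contrast only if they went with genotype, and nothing in the documents suggests that.
- **Absolute CSF concentration is itself part of the primary outcome.** It needs no binding correction, and it is the quantity closest to the concern in 2.1 about reaching an effective concentration at the site of action.
- **Samples are not at equilibrium.** Each subject gives one CSF sample, with the infusion timed about 30, 60 or 120 min before needle insertion (2.5.2). Dividing a raw ratio by fu does not remove that time dependence, so the correction belongs in the model.
- **The second vial is not described as spare.** Section 2.5.2 sends both vials for HPLC-MS.

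The reply does not remove the ambiguity in absolute size. The genotype contrast is relative: in 15 subjects and ten SNPs it does not say how large any penetration deficit is. The plan also sets no rule for reading a ratio that it places in the primary outcome.

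**Conclusion.** The point holds for the absolute size of the total CSF:plasma ratio and the plasma-CSF partition coefficient. It does not extend to CSF concentrations, or to genotype contrasts under a common unbound fraction. On the plan's expected values, a ratio of 0.075-0.10 fits an unbound ratio of 0.75-1.00 at an assumed fraction of 0.1 and 0.15-0.20 at 0.5.

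This rests on CSF drug being close to unbound, on plasma being assayed as total drug (inferred from the absence of any separation step), and on pairing the expected ranges low with low and high with high. The correction is small if binding is slight: at a fraction of 0.8 the unbound ratio is 0.09-0.13.

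A reader might go further and infer that the low ratio is nothing but binding. The documents give no unbound fraction to support that, and at assumed fractions of 0.2 or more a deficit of at least 2-fold remains under that pairing. This is a limit on interpretation that is cheap to remove. The measurements themselves remain usable.

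**What to change.** Change 2.5.4.1 and 2.5.4.3, and align the Statistical Methodology row of the Synopsis:

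1. Keep the total CSF:plasma ratio, labelled as descriptive.
2. In the population model, scale the plasma input to the CSF compartment by the unbound fraction. Report the partition coefficient on an unbound basis beside the total one. The model already has to account for sampling time, so this is preferable to dividing single-sample ratios.
3. State the source of the fraction before the data are seen: one referenced value with a sensitivity range. If stored plasma volume remains after the HPLC-MS assay, a fraction measured in a pooled sample or in one sample per subject (up to 15 assays) could replace it.
4. Add a sentence that the total-plasma ratio alone will not be read as evidence of transporter-limited penetration.

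With a stated fraction, the cost is wording, one scaling factor and a sensitivity table. With a measured fraction, it is a small amount of bench work and no extra patient procedure. The downsides are that the unbound result depends on an assumption unless the fraction is measured, and that the penetration deficit will look smaller than the raw ratio suggests.

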### **2.5.3 Minimization of Bias**

There will be no specific sex, ethnic or racial background for enrollment. Plasma and CSF ondansetron concentration is not affected by subjects' or investigators' knowledge of study aims and hypothesis.

### **2.5.4 Observations and Measurements**

#### **2.5.4.1 Primary Outcome Measures**

##### Primary outcome:

Plasma and CSF concentrations of ondansetron, and CSF to plasma concentration ratio.

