Ondansetron may cause QT interval prolongation in rare cases; therefore, the subjects' heart rhythm will be monitored throughout the infusion and for approximately 30 min after the end of infusion using standard 4 lead monitors in the holding area. No changes will be made to the routine intraoperative management and hemodynamic physiological monitoring, with the exclusion of the PK blood sampling period.

The DNA isolation and genotyping will include analysis of single nucleotide polymorphisms (SNPs) in OCT1 and P-glycoprotein transporters. We will genotype for the following five P-glycoprotein (ABCB1) SNPs: C3435T, T-129C, G1199A, C1236T, G2677T [11-14], and for five OCT1 (SLC22A1) SNPs: R61C, C88R, G401S, M420del, or G456R that have reported to affect ondansetron pharmacokinetics or clinical antiemetic effect. The genotyping will be performed at Washington University Genome Technology Access Center. The whole blood samples will be extracted using the QIAamp DNA mini Blood kit (QIAGEN). The DNA will be quantified and quality controlled using nanodrop and gel readings. The SNPs will be interrogated using Taqman probes (Applied Biosystems). Each SNP will have its own 20µl reaction well with a final

concentration of 1X Taqman probe mix, 1X Taqman PCR master mix, and 20-40ng of DNA. The samples will be cycled and analyzed on CFX96 Real-time PCR Detection System (Bio-Rad). The collected blood and DNA samples will be de-identified and coded to ensure patient confidentiality and HIPPA compliance.

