#### **2.5.4.2 Secondary Outcome Measures**

##### Secondary outcomes:

Non-compartmental modeling to determine plasma PK parameters of ondansetron – i.e. volume of distribution (Vd), clearance (CL), maximum CSF and plasma concentration (Cmax), and the time to reach these maximum concentrations (Tmax).

Compartmental modeling using population PK approach to determine CSF pharmacokinetic parameters of ondansetron.

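### Does the primary CSF:plasma ratio need a stated plasma denominator and a start-or-end reference for the 30/60/120-min CSF interval?

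*Combined protocol and SAP*

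**What the plan says.** Section 2.5.4.1 defines the primary outcome in one line: "Plasma and CSF concentrations of ondansetron, and CSF to plasma concentration ratio". It gives no rule for choosing or matching the plasma value.

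Section 2.5.2 supplies the timing:

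- Dose: "Ondansetron will be administered in a 16mg single dose as a 15 min intravenous infusion".
- CSF: one sample per subject at needle insertion, where "the timing of the infusion will be scheduled at approximately 30, 60, or 120 min before planned pre-surgical spinal needle insertion". The stated purpose is coverage over time: "This will allow 3 time-points of CSF samples from the aggregate study cohort".
- Plasma: samples at 0, 15, 30, 60, 120 and 180 min, timed "from the beginning of infusion in each patient, regardless of timing for CSF sampling".
- ECG monitoring: during the infusion and "for approximately 30 min after the end of infusion".
- CSF analysis: "The CSF ondansetron pharmacokinetic profile will be constructed using population PK approach, according to the exact time of CSF sampling".

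Section 2.5.4.2 lists the CSF modelling as a secondary outcome: "Compartmental modeling using population PK approach to determine CSF pharmacokinetic parameters of ondansetron". Section 2.5.4.3 adds that the model has a CSF compartment, estimates the plasma-to-CSF partition coefficient and yields parameters for individual patients. The Synopsis lists the same plasma times but counts them only from ondansetron administration, without saying start or end.

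**The concern.** A primary outcome should be computable in only one way. Here each subject gives one CSF value and five plasma values after the infusion begins, and the plasma schedule is explicitly not tied to the CSF draw. From the same data the ratio could use the nominal plasma sample, an interpolated value or a model-predicted value.

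The missing reference point appears to make this worse. Because the infusion lasts 15 min, counting from its end puts the nominal CSF draws at 45, 75 and 135 min on the plasma clock, where no plasma sample is scheduled. The exact-time rule is written for the population model, which is secondary, so it does not formally define the primary ratio. If analysts paired mismatched nominal samples, the ratio would be biased, most of all in the earliest timing group, where plasma falls fastest.

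**Working it through.** **Inputs from the documents.** Infusion 16 mg over 15 min; plasma draws at 15, 30, 60, 120 and 180 min from its start; nominal CSF intervals 30, 60 and 120 min; 15 evaluable subjects; expected plasma range 40–120 ng/mL (all in section 2.5.2 except the number of subjects, section 2.4).

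**Step 1: the plan's own figure.** 15 subjects / 3 timing groups = 5 per group, as section 2.5.2 states approximately.

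**Step 2: the two readings on the plasma clock.**

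| Reading | Nominal CSF times (min from start) | Scheduled plasma draw at that time? |
|---|---|---|
| From start of infusion | 30, 60, 120 | Yes, all three |
| From end of infusion | 30+15 = 45, 60+15 = 75, 120+15 = 135 | None |

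Under the first reading an on-time draw has zero timing error, and the nominal, interpolated and measured plasma values are the same number.

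**Step 3: error if a mismatched nominal sample were used.** The computed ratio is CSF / C(nominal) and the target is CSF / C(actual), so the relative error is C(actual)/C(nominal) − 1.

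*Expected range only.* The protocol gives the range without times. Assume a log-linear fall from 120 ng/mL at 15 min to 40 ng/mL at 180 min. Then k = ln(120/40)/165 = 0.00666 per min.

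- 5 min late: exp(−5k) − 1 = −3.3%. 5 min early: exp(5k) − 1 = +3.4%.
- 15 min late: exp(−15k) − 1 = −9.5%. 15 min early: exp(15k) − 1 = +10.5%.

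*Two-compartment profiles.* Section 2.5.4.3 expects two-compartment disposition but gives no parameters. Four assumed sets, CL/V1/Q/V2 in L/h and L, roughly match the expected range: 30/125/60/60, 30/120/40/40, 25/130/60/50 and 35/120/60/60. They give C(15) = 117.7, 124.5, 114.2 and 121.6 ng/mL, and C(180) = 49.9, 54.3, 56.5 and 45.9 ng/mL. Errors across the four sets:

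| Mismatch | 30-min group | 60-min group | 120-min group |
|---|---|---|---|
| 5 min late | −3.7 to −4.9% | −2.4 to −3.5% | −1.4 to −2.0% |
| 15 min late | −10.0 to −13.2% | −6.8 to −9.5% | −4.1 to −5.8% |
| 15 min early | +13.5 to +18.3% | +8.9 to +12.6% | +4.6 to +6.8% |

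The 15-min-late row is the start/end ambiguity: a draw counted from the end of infusion but paired with the 30-, 60- or 120-min plasma sample.

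**Step 4: error if plasma is interpolated to the actual CSF time.** Log-linear interpolation between the planned samples, same four profiles:

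| CSF time (min) | Ratio error |
|---|---|
| 45 | −0.7 to −1.1% |
| 75 | −1.2 to −1.8% |
| 135 | −0.3 to −0.5% |
| Worst point in 15–180 (about 87 min) | −1.5 to −2.2% |

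Linear interpolation leaves at most 3.5%. All nominal CSF times, under either reading, lie inside 15–180 min, so bracketing samples exist. The planned model can supply a plasma value for a draw outside that window.

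**Step 5: what depends on the ratio.** Sections 2.3 and 2.5.5 describe a feasibility pilot sized by custom for pharmacokinetic studies. The documents attach no hypothesis test, decision threshold or power calculation to the ratio.

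**The case for a change.** The strongest argument for a change is that a sound secondary model does not define a primary outcome, and that the wording excludes no denominator at all. If peak plasma were used, the 120-min ratio would be about half the time-matched one: on the log-linear profile, 120/59.6 = 2.0, and on the four two-compartment profiles, 1.7 to 2.1. The ratio may also rise with time if CSF lags plasma, so pooling the three timing groups would mix different quantities. A short definition would cost nothing in blood, subjects or assays.

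Part of this stands. The denominator is unstated, and the exact-time rule is written for the model only. The Synopsis wording for plasma times is as loose as the wording for the CSF interval, so the missing reference point is not peculiar to CSF.

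The twofold effect, however, needs a denominator that no section suggests. Section 2.5.4.1 names plasma and CSF concentrations and then their ratio, which reads most naturally as concentrations at the same time. Any lag of CSF behind plasma is what the three timing groups and the CSF compartment are there to describe. It does not show that the denominator will be chosen badly. Among time-matched choices (measured, interpolated or model-predicted plasma), the interpolation errors in Step 4 are small.

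**Conclusion.** No change to the plan follows. This is missing detail that a pharmacokinetic analyst would fill sensibly: take the plasma concentration at the recorded CSF time, and show ratios against time or by timing group. The plan already supplies what that needs, namely serial plasma samples around the CSF draw, use of the exact CSF time in the model, and a nominal schedule that coincides with plasma draws under the natural reading.

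The effect is zero for an on-time draw counted from the start of infusion, and at most about 2.2% with log-linear interpolation (3.5% with linear). It reaches about 4 to 18% only if a nominal plasma sample 15 min away is used, which the documents do not propose. These percentages rest on assumed plasma profiles fitted loosely to the expected 40–120 ng/mL, because the protocol gives no disposition parameters. With about five subjects per timing group and no inference on the ratio, errors of a few percent would not alter what the pilot can conclude. A sentence naming the denominator and a single time origin would be tidy but optional.
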